16.12. Subject Discontinuation

A subject may be removed from the study prior to completion for any of the following reasons:

- Voluntary withdrawal of consent
- Adverse event preventing further study participation
- Investigator believes risk of further subject participation outweighs benefit
- Persistent non-compliance or lost to follow-up
- Pregnancy
- Subject no longer meets inclusion criteria
- Reduced opioid dosage is not tolerable, as evaluated by the subject or the investigator
- Subject fails to comply with reduced opioid dosage
- Subject changes dosage of non-opioid medications known to interfere with sleep or RLS symptoms, including sleep medications, antidepressants, sedative antihistamines.

The Investigator or research staff will complete a study exit form in the CRF for any subject who prematurely discontinues from the study. If discontinuation was the result of an AE, the AE will also be recorded in the CRF.

Upon discontinuation, subjects will receive partial compensation commensurate with their completed Phases.

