17.2.1. Safety Endpoints

Endpoint 1: Frequency of Grade 2 of higher NPNS-related adverse events, as indicated by a relatedness assessment of Probable or Definite.

Endpoint 2: Frequency of Grade 3 or higher NPNS-related adverse events.

Endpoint 3: Percentage of subjects who withdraw from study during Phase 1 or Phase 2 citing lack of tolerability of NPNS as the primary reason for withdrawal.

Endpoint 4: Percentage of subjects who are discontinued from study due to non-RLS opioid withdrawal symptoms during Phases 1 or 2.

Endpoint 5: Percentage of subjects who withdraw from study citing lack of tolerability of NPNS as the primary reason for withdrawal during Phase 1

Endpoint 6: Percentage of subjects who withdraw from study citing lack of tolerability of NPNS as the primary reason for withdrawal during Phase 2.

Endpoint 7: Percentage of subjects who are discontinued from study due to non-RLS opioid withdrawal symptoms during Phase 1.

Endpoint 8: Percentage of subjects who are discontinued from study due to non-RLS opioid withdrawal symptoms during Phase 2.

Additional exploratory endpoints:

CONFIDENTIAL

All information contained in this document is confidential and is the sole property of Noctrix Health, Inc.
Any reproduction in part or whole without the written permission of Noctrix Health, Inc. is prohibited.

 NOCTRIX HEALTH	Clinical Trial Investigational Plan, Protocol CT-03 (Opioid Reduction Study)	Document #: CT-2 (Previously CT-03) Rev: 4.0 (Superseded Rev C) CC#: 720 (Previously DCO #138) Effective: 09/24/2021
---	---	---

Endpoint 9: Reduction in severity of side-effects related to opioid use (not withdrawal) that were present at baseline during Phase 1 and Phase 2 assessment periods.

** Note that data from the Extension Phase is included in analysis of Endpoints 1 and 2 but not analysis of Endpoints 3-9.*

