17.3. NPNS Tolerability

NPNS tolerability will be quantified based on the percentage of participants who voluntarily withdraw from the study prior to the Extension Phase citing lack of tolerability of NPNS treatment as the primary reason for withdrawal, as quantified by selection of response #3 on a questionnaire similar to the one below.

Primary reason for withdrawal:

- I want to return to my original opioid dosage because:
 - (1) my RLS symptoms have gone up after I reduced my opioid dosage
 - (2) I experienced other opioid withdrawal symptoms after I reduced my opioid dosage
- (3) Use of the NPNS devices was uncomfortable or otherwise intolerable
- (4) Other

CONFIDENTIAL

All information contained in this document is confidential and is the sole property of Noctrix Health, Inc.
 Any reproduction in part or whole without the written permission of Noctrix Health, Inc. is prohibited.

 NOCTRUX HEALTH	Clinical Trial Investigational Plan, Protocol CT-03 (Opioid Reduction Study)	Document #: CT-2 (Previously CT-03) Rev: 4.0 (Superseded Rev C) CC#: 720 (Previously DCO #138) Effective: 09/24/2021
---	---	---

The criterion for success will be fewer than 20% of subjects who begin NPNS treatment withdrawing for this reason.

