17.4. Compliance

Compliance will be measured based on digital tracking of the timing and duration of each NPNS device usage during the Assessment weeks of Phase 1 and Phase 2. A “*night of compliant use*” will be defined as a minimum of 25 minutes of active NPNS stimulation between 5pm and 8am during an Assessment week. “*Total assessment nights*” will be defined as the total nights spent by all subjects in Assessment weeks. “*Total assessment nights with RLS symptoms*” will be defined as the total nights spent by all subjects in Assessment weeks when the subject reports RLS symptoms on the Daily questionnaire. If a subject is removed from the study before the end of an Assessment week, such as due to an adverse event or for personal reasons, data from that Assessment week will not be included in the compliance analysis. In cases where digital tracking logs are incomplete or unavailable, the data will not be included in the compliance analysis.

- For participants who are instructed to administer stimulation each night, percentage compliance will be calculated using the following formula:
 - $100\% * (\text{nights of compliant use}) / (\text{total assessment nights})$
- For participants who are instructed to administer stimulation only on nights with RLS symptoms, percentage compliance will be calculated using the following formula:
 - $100\% * (\text{nights of compliant use}) / (\text{total assessment nights with RLS symptoms})$

The global criterion for success will be percentage compliance of $\geq 70\%$, based on the weighted average of individual compliances (i.e. weighting nights equally instead of weighting participants equally).

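### NPNS tolerability counts only subjects who leave the study citing it, so stopping the device for discomfort while staying enrolled is scored as tolerating it, and the compliance criterion does not reliably catch this

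*Combined protocol and SAP*

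**What the plan says.** Section 17.3 defines the measure: "NPNS tolerability will be quantified based on the percentage of participants who voluntarily withdraw from the study prior to the Extension Phase", with the reason taken from the withdrawal questionnaire, "as quantified by selection of response #3 on a questionnaire similar to the one below". Response #3 is the one for devices that were uncomfortable or otherwise intolerable. The pass rule is: "The criterion for success will be fewer than 20% of subjects who begin NPNS treatment withdrawing for this reason". The denominator is therefore everyone who starts NPNS, and the numerator is voluntary withdrawals with that one response.

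Section 17.2.1 follows the same logic. Safety Endpoint 3 is: "Percentage of subjects who withdraw from study during Phase 1 or Phase 2 citing lack of tolerability of NPNS as the primary reason for withdrawal". Endpoints 5 and 6 split it by Phase, and the synopsis entry on tolerability is also based on withdrawal.

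The only criterion on device use is in Section 17.4: "The global criterion for success will be percentage compliance of" at least 70%, "weighting nights equally instead of weighting participants equally". A compliant night needs a "minimum of 25 minutes of active NPNS stimulation between 5pm and 8am during an Assessment week". There is no minimum per subject and no reason for non-use is recorded. Weeks cut short by removal, and data with incomplete logs, are left out.

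Section 16.12 lists "Persistent non-compliance or lost to follow-up" among the reasons for which a subject may be removed. Removal is permitted, not required, and no usage threshold is given.

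**The concern.** Stopping use is the most direct sign that a self-administered device is not tolerated, and here it does not enter the tolerability result. The route is open under the plan's own rules. Subjects treat themselves at home (Section 16.7). Advancement depends on CGI-I and on tolerating the opioid reduction, with no condition on device use (Section 13.1). Compensation follows completed Phases (Section 16.12), which gives some reason to stay enrolled.

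Three kinds of subject who could not tolerate the device are scored as if they could:

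- one who stops using it and completes both Phases;
- one whom the investigator removes for non-compliance, since that is not a voluntary withdrawal with response #3;
- one who stops it for discomfort, then has more RLS symptoms and leaves giving response #1 as the primary reason.

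Each stays in the denominator and none enters the numerator, so the error goes in one direction: the percentage is too low. At stake is a pre-specified success criterion. Section 1.5 says the in-home design is meant to find every barrier to tolerable use.

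**Working it through.** The plan states no figure for non-use and no derivation of the 20% limit, so there is nothing to reproduce. The check applies the two pass rules to subjects who stop the device but do not withdraw.

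**Inputs from the plan.** Tolerability passes if response-#3 withdrawals / subjects starting NPNS < 20% (17.3). Compliance passes if compliant nights / counted assessment nights ≥ 70%, pooled over nights (17.4). There is one assessment week per Phase, so nominally 7 nights for one Phase and 14 for two (13.2). Enrolment is 20–40 (synopsis).

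**Assumptions not in the plan.** The compliance c of the remaining users, and how nights are split between stoppers and users.

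**Step 1: tolerability.** If a share f stops but stays enrolled, the numerator is 0 and tolerability reads 0% for any f.

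**Step 2: compliance with equal nights and nightly instruction.** If stoppers use nothing in any assessment week, pooled compliance is (1 − f) × c. This passes when f ≤ 1 − 0.70/c.

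| c (others) | Largest f that passes |
|---|---|
| 100% | 30.0% |
| 95% | 26.3% |
| 90% | 22.2% |
| 87.5% | 20.0% |
| 85% | 17.6% |
| 80% | 12.5% |
| 70% | 0% |

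The break-even with the plan's own limit solves 1 − 0.70/c = 0.20, so c = 0.70/0.80 = 87.5%. Below that, compliance fails before silent stoppers reach 20%.

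Example: 5 of 20 stop (25%). Tolerability is 0/20, a pass. Compliance is 15/20 = 75% at c = 100%, or 0.75 × 0.95 = 71.25% at c = 95%, a pass in both cases.

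**Step 3: unequal nights or late stopping, with all others fully compliant.**

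- Stoppers leave after Phase 1 (7 nights) and users give 14: 14(1 − f) ≥ 0.70 × [14(1 − f) + 7f], so f ≤ 4.2/9.1 = 46.2% (9 of 20, or 18 of 40).
- Stoppers give 14 nights and users 7: 7(1 − f) ≥ 0.70 × [7(1 − f) + 14f], so f ≤ 2.1/11.9 = 17.6% (3 of 20, or 7 of 40).
- Stoppers use the device fully in Phase 1 and not at all in Phase 2: 14(1 − f) + 7f ≥ 0.70 × 14, so f ≤ 4.2/7 = 60% (12 of 20, or 24 of 40).

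**Step 4: stoppers and withdrawals together, equal nights, others fully compliant.** With 20 subjects, 3 may withdraw with response #3 before any counted assessment week (15%, a pass). Of the 17 left, 5 may be silent stoppers (12/17 = 70.6%, a pass). That is 8/20 = 40% with both criteria passing.

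**Step 5: if stoppers are counted.** The 5-of-20 example reads 25% and fails. The most that could pass is 3/20 (15%) or 7/40 (17.5%).

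**The case against.** The strongest reply has four parts.

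**Dependence on good use by the others.** A reader might infer that up to 30% of subjects can always abandon NPNS with both criteria passing. The plan does not support this. The 70% rule limits pooled nights, not subjects. The 30% figure needs equal nights, no use at all by stoppers, and perfect use by everyone else. At 85% compliance among the others the limit is already below 20%. This stands, and any percentage has to carry its conditions.

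**Symptom-based use.** Section 16.7 instructs treatment on nights with symptoms, and 17.4 has a separate denominator for those users. Section 17.1 expects symptoms to rise when the opioid dose falls without an adjunct. Stoppers may therefore have more counted nights, and compliance would fail sooner. This also stands; it is the direction of the 17.6% case in Step 3.

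**A third criterion exists.** Section 17.2.3 requires no Grade 3 or higher device-related adverse events and fewer than 20% of subjects with Grade 2 events. Discomfort that reaches Grade 2 can count there. Grade 1 discomfort that is enough to make someone stop is not limited by it. The plan also names anticipated observations, which include stimulation discomfort, separately from adverse events (Sections 6.1 and 7). The gap is narrowed, not closed.

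**Non-use is unlikely and visible.** Calibration excludes some intolerant subjects, intensity can be lowered, and device use is reviewed at the follow-up evaluations. A reader might infer that abandonment would go unseen, or that a quarter of subjects can be expected to stop. Neither follows: use is logged and discussed, and the plan gives no expected rate. What remains is that none of this information feeds the tolerability result.

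Reporting withdrawal for intolerance and compliance separately is a possible choice in an exploratory study. It does not make the withdrawal figure a measure of tolerability, which is how 17.3 uses it.

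**Conclusion.** The concern holds as a defect of definition. Section 17.3 and Safety Endpoints 3, 5 and 6 miss subjects who stop NPNS for discomfort without a voluntary withdrawal citing it. The tolerability percentage can only be lowered by this, and it reads 0% for any number of silent stoppers. That part rests on the text alone.

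The size depends on assumptions. In the equal-nights, nightly-instruction model, compliance and tolerability both pass with more than 20% abandoning only if the remaining users comply on more than 87.5% of nights. Over the unequal-night and late-stopping cases tried, with full compliance by the others, the limit runs from about 18% to 60%. These figures show what the rules would let through, not what is likely to happen.

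The change should be made, because the rule can turn a stated success criterion in the favourable direction. It does not touch the primary endpoint.

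**What to change.** In Section 17.3 and Safety Endpoints 3, 5 and 6, count as NPNS-intolerant any subject who begins NPNS and, before the Extension Phase (for Endpoints 5 and 6, in the relevant Phase), either withdraws with response #3 or permanently stops NPNS because it is uncomfortable or intolerable, whether or not the subject leaves the study.

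- **Finding stoppers.** Flag from the device log any subject with no compliant night in an assessment week. For subjects told to use the device only on symptom nights, apply the flag only if symptom nights were reported. Where logs are missing, use the daily questionnaire.
- **Reason.** Add one item on the reason for non-use to the device-use reviews already held under Section 16.9. The flag alone does not make a subject intolerant; the reason does.
- **Criterion.** Apply the limit of fewer than 20% to this count, and report the withdrawal-only percentage as a component. The plan gives no derivation for 20%, so the sponsor should confirm that it is meant for the wider count.

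The cost is a wording change in two sections and one added question. The data sources exist, and no treatment or removal rule changes. The downside is that the tolerability figure may be less favourable.

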17.4. Compliance

Compliance will be measured based on digital tracking of the timing and duration of each NPNS device usage during the Assessment weeks of Phase 1 and Phase 2. A “*night of compliant use*” will be defined as a minimum of 25 minutes of active NPNS stimulation between 5pm and 8am during an Assessment week. “*Total assessment nights*” will be defined as the total nights spent by all subjects in Assessment weeks. “*Total assessment nights with RLS symptoms*” will be defined as the total nights spent by all subjects in Assessment weeks when the subject reports RLS symptoms on the Daily questionnaire. If a subject is removed from the study before the end of an Assessment week, such as due to an adverse event or for personal reasons, data from that Assessment week will not be included in the compliance analysis. In cases where digital tracking logs are incomplete or unavailable, the data will not be included in the compliance analysis.

- For participants who are instructed to administer stimulation each night, percentage compliance will be calculated using the following formula:
 - $100\% * (\text{nights of compliant use}) / (\text{total assessment nights})$
- For participants who are instructed to administer stimulation only on nights with RLS symptoms, percentage compliance will be calculated using the following formula:
 - $100\% * (\text{nights of compliant use}) / (\text{total assessment nights with RLS symptoms})$

The global criterion for success will be percentage compliance of $\geq 70\%$, based on the weighted average of individual compliances (i.e. weighting nights equally instead of weighting participants equally).

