5.2.2. Dosage and dosage regimen

The dosage depends on the intensity and duration of stimulation:

1. Setpoint stimulation intensity. The setpoint stimulation intensity will be the lesser of (a) the maximal intensity that the subject reports is non-distracting and comfortable, as determined in the calibration session described in the instructions for device use and (b) the maximal intensity for each set of stimulation parameters, as determined based on device output capabilities.
2. Participants will be allowed to adjust stimulation intensity from the setpoint, but only within a limited pre-programmed range. For example, participant may increase intensity if symptoms are severe or reduce intensity if symptoms are mild.
3. Participants may be instructed to administer stimulation each night or only administer stimulation when RLS symptoms are present.
4. Stimulation may be activated for up to 120 minutes per day, depending on the timing, duration, and severity of RLS symptoms for the specific subject.

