16.7. Study Treatment Description

Study subjects are instructed to self-administer treatment for at least 30 minutes on each night that they experience RLS symptoms. Study subjects may self-administer up to four 30-min sessions per day, as needed based on RLS symptoms. The instructions for timing of these "as needed" doses will be determined at the discretion of the investigator and research staff, based on the RLS symptoms experienced by the subject.

CONFIDENTIAL

 NOCTRIX HEALTH	Clinical Trial Investigational Plan, Protocol CT-03 (Opioid Reduction Study)	Document #: CT-2 (Previously CT-03) Rev: 4.0 (Superseded Rev C) CC#: 720 (Previously DCO #138) Effective: 09/24/2021
---	---	---

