In addition to these assessments, the devices automatically log quantitative compliance, usage data, and leg movement data throughout the duration of the study.

The following are completed by subject: IRLS, Daily questionnaire, Medication use assessment, Step-down assessment questionnaire.

The following are administered and completed by the investigator or designee: Screen for inclusion/exclusion, Informed consent, Study entry questionnaire, CGI-I, Opioid-related symptom assessment, AE assessment.

CONFIDENTIAL

All information contained in this document is confidential and is the sole property of Noctrix Health, Inc.
 Any reproduction in part or whole without the written permission of Noctrix Health, Inc. is prohibited.

 NOCTRIX HEALTH	Clinical Trial					Document #: CT-2 (Previously CT-03) Rev: 4.0 (Superseded Rev C) CC#: 720 (Previously DCO #138) Effective: 09/24/2021				
	Investigational Plan, Protocol CT-03 (Opioid Reduction Study)									

Table 5A. Schedule of Assessments

	Baseline		Opioid Reduction Phase 1				Opioid Reduction Phase 2				Exit or Extension	
			Acclimate to Opioid Reduction (7-14 days)				7 days from last Eval (3, 4, or 5)	Acclimate to Opioid Reduction (7-14 days)				
	Pre-screening	Eval. #1 (clinic visit)	Eval. #2 (call) 3-days	Eval #3 (call) 7-days	Eval. #4 (call)* 10-days	Eval #5 (call)* 14-days		Eval. #6 (call or visit) End of Phase 1/ Start of Phase 2	Eval. #7 (call) 3-days	Eval #8 (call) 7-days	Eval. #9 (call)* 10-days	Eval #10 (call)* 14-days
Pre-screen inclusion/exclusion	X											
Screen inclusion/exclusion		X										
Informed consent		X										
Study entry questionnaire		X										
NPNS calibration & IFU training		X										
Dispense NPNS Device		X										
Calculate baseline opioid dose		X										
Incremental Opioid Dose Reduction		X						X				O
Review Daily Questionnaire			X	X	O	O	X	X	X	O	O	X
CGI-I							X					X
IRLS		X		X		O	X		X		O	X
Medication use assessment			X	X	O	O	X	X	X	O	O	X
Opioid withdrawal assessment		X		X	O	O	X	X	X	O	O	X
AE assessment				X		O	X		X		O	X
Step-down assessment questionnaire							X					X

*(O) = Optional, if additional time for adjusting to opioid reduction is needed.

Table 5B. Extension Phase Schedule of Assessments

	Opioid Reduction Phase 3 (Optional)				Study Exit	
	Acclimate to Opioid Reduction (7-14 days)				7 days from last Eval (13, 14 or 15)	

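### For participants told to stimulate only on symptom nights, the Section 17.4 compliance ratio counts compliant nights of any kind over reported symptom nights, so it can be inflated and can exceed 100%

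*Combined protocol and SAP*

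**What the plan says.** Section 17.4 defines a night of compliant use by stimulation time and clock window only: it "will be defined as a minimum of 25 minutes of active NPNS stimulation between 5pm and 8am during an Assessment week". The definition does not mention symptoms or a completed diary.

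Two formulas use that count unchanged. For participants told to stimulate every night, the denominator is all Assessment nights. The second formula is introduced by "For participants who are instructed to administer stimulation only on nights with RLS symptoms, percentage compliance will be calculated using the following formula", and its denominator is the "total nights spent by all subjects in Assessment weeks when the subject reports RLS symptoms on the Daily questionnaire".

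The two counts come from different sources. Section 16.9 says that "the devices automatically log quantitative compliance, usage data, and leg movement data throughout the duration of the study", and also that "The following are completed by subject: IRLS, Daily questionnaire, Medication use assessment, Step-down assessment questionnaire". The only missing-data rule in Section 17.4 for individual records concerns the device: "In cases where digital tracking logs are incomplete or unavailable, the data will not be included in the compliance analysis".

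On who falls under the second formula, Section 5.2.2 says "Participants may be instructed to administer stimulation each night or only administer stimulation when RLS symptoms are present", while Section 16.7 says "Study subjects are instructed to self-administer treatment for at least 30 minutes on each night that they experience RLS symptoms". No split between the two instructions is given.

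The global success criterion in Section 17.4 is compliance of at least 70%, as an average of individual compliances in which nights, not participants, carry equal weight. The synopsis describes the compliance endpoint as device use on symptom nights in the Phase 1 and Phase 2 Assessment periods.

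**The concern.** For symptom-only users the numerator is not a subset of the denominator. Two kinds of night add to the top and not to the bottom:

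- **A symptom-free night with compliant use.** This departs from the participant's instruction, yet it earns credit that can offset a missed symptom night.
- **A night with compliant use but no diary entry.** The participant may have treated a real symptom night exactly as told. The device logs the use, but the night never enters the denominator.

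The error has one direction for these participants: the ratio equals or overstates the share of reported symptom nights with compliant use. Near 70% the criterion could be met where a matched ratio would miss it. In the global average, individual values above 100% can offset low compliance elsewhere. The share of participants exposed is unknown and could be anything up to all of them.

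**Working it through.** The plan states no expected compliance, so there is no figure to reproduce; 70% is a threshold. From the documents come the two definitions, the 7-night Assessment week (Section 13.2) and the threshold. Every night count and rate below is assumed.

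**Formulas.** Let S be reported symptom nights, a the compliant nights among them, and c the compliant nights outside them (symptom-free or no diary).

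- As written: 100 × (a + c)/S
- Matched: 100 × a/S, which cannot exceed 100%
- Excess: 100 × c/S, which is zero when c = 0

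**Ceiling in a 7-night week, 7/S.** S = 6 gives 116.7%, S = 5 gives 140%, S = 4 gives 175%. Only S = 7 is bounded at 100%. The every-night formula divides by all nights and cannot exceed 100%.

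**Missing diary, no use against instruction.** Assume symptoms on all 14 Assessment nights of the two Phases, 2 nights without a diary entry, and 9 compliant nights, so S = 12. As written: 9/12 = 75.0%. With k of the no-diary nights compliant, the matched ratio is (9 − k)/12:

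| k | As written | Matched |
|---|---|---|
| 0 | 75.0% | 75.0% |
| 1 | 75.0% | 66.7% |
| 2 | 75.0% | 58.3% |

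**Use on symptom-free nights.** If compliant use occurs on a fraction q of the 7 − S other nights, the excess is q(7 − S)/S:

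| S | q = 0.1 | q = 0.3 |
|---|---|---|
| 6 | 1.7 points | 5.0 points |
| 4 | 7.5 points | 22.5 points |

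**Global figure.** Let f be the share of participants who are symptom-only, and weight each participant by denominator nights. The excess over the corrected formula is f·q(7 − S)/(f·S + 7(1 − f)):

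| f | S = 6, q = 0.1 | S = 4, q = 0.3 |
|---|---|---|
| 0.25 | 0.025/6.75 = 0.4 points | 0.225/6.25 = 3.6 points |
| 0.5 | 0.05/6.5 = 0.8 points | 0.45/5.5 = 8.2 points |
| 1 | 0.1/6 = 1.7 points | 0.9/4 = 22.5 points |

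**How little is needed to cross 70%.** Take 20 symptom-only subjects × 14 nights = 280 nights, with 60% matched compliance. With 160 symptom nights, 96 are compliant and 112 are needed, so 16 of the other 120 nights (13.3%) suffice. With 200 symptom nights, 120 are compliant and 140 are needed, so 20 of the other 80 (25%) suffice.

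**Against the synopsis endpoint.** Here the direction of the global figure is not fixed, because every-night users are divided by all nights. Take one user of each type, with S = 4.

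- Both use the device on 65% of symptom nights; use on other nights is 30% (symptom-only) and 65% (every-night). Section 17.4 gives (2.6 + 0.9 + 4.55)/11 = 73.2%, against 5.2/8 = 65.0% on symptom nights.
- Both use it on 80% of symptom nights; use on other nights is 10% and 50%. Section 17.4 gives (3.5 + 4.7)/11 = 74.5%, against 6.4/8 = 80.0%.

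**The case against.** **Intent.** The synopsis ties use to symptom nights, so an analyst might restrict the numerator without being told. That supports the correction. It does not change Section 17.4, where compliant use is a defined term applied unchanged in both formulas.

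**Existing controls.** Table 5A schedules diary review at the calls and at the end-of-Assessment evaluations, Section 10.6 has monitors check completeness, and Section 10.8 requires discrepancies to be resolved before database lock. These make unnoticed gaps less likely, but none says how a no-diary night is to be analysed.

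**Size.** The population has moderate-to-severe RLS and is reducing opioids, which Section 17.1 expects to increase symptoms without adjunctive treatment. Symptom-free nights may be few, and nothing in the documents supports 4 symptom nights of 7 with 30% use on the others. This stands: the upper figures are illustrations, and the true excess may be zero.

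**The matched ratio is not the truth either.** In the missing-diary example the true rate is 9/14 = 64.3%. The matched ratio is 10.7 points above it at k = 0 and 6.0 below it at k = 2. This also stands: the correction measures compliance on diary nights only, which is why the dropped nights must be shown.

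**Weighting.** Equal weighting of nights could mean all Assessment nights rather than denominator nights. Then with S = 4 and q = 0.3 the global excess is 0.25 × 22.5 = 5.6 points at f = 0.25 and 0.5 × 22.5 = 11.3 at f = 0.5. The global sizes therefore depend on a reading that the plan leaves open; the defect does not.

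**Visibility.** An individual value above 100% would be noticed in reporting. A pooled figure just above 70% would not.

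**Conclusion.** The concern holds. Applied as written, the symptom-only formula can exceed 100% and can only equal or overstate compliant use on reported symptom nights. This is an error in the definition, not just missing detail.

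Its size cannot be fixed from the documents, which give no number of symptom-only participants, symptom-night frequency or diary completion rate. At the individual level it depends only on the ratio of compliant nights outside reported symptom nights to reported symptom nights. The global size also depends on the symptom-only share and the weighting.

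The consequence is limited. This is a supporting criterion in an exploratory study, and the primary (17.1.5), safety (17.2.3) and tolerability (17.3) criteria do not use it. It should still be corrected, because it decides a stated pass or fail.

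**What to change.** In Section 17.4, for symptom-only users:

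- Count in the numerator only nights that are both compliant and reported as symptomatic on the Daily questionnaire.
- Take numerator and denominator over nights with both a diary entry and a device log.
- Report the number of nights dropped for a missing diary.

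Secondary wording: align the synopsis with Section 17.4 (the 25-minute, 5pm to 8am definition, and all nights for every-night users), state that each participant is weighted by denominator nights, and report participants with no symptom nights separately, since their ratio is undefined.

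The cost is a few sentences in Section 17.4 and one in the synopsis. No new data are needed, because the device log and nightly diary are already collected. Reported compliance may come out lower. Dropping no-diary nights can also bias the figure: upward if subjects who skip the diary also skip the device, downward if they treat on the nights they do not record. The dropped count lets readers judge this.
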